Final eligibility will be determined by the investigator after review of the medical record and data gathered during the screening visit. Eligible, enrolled subjects will undergo additional baseline procedures:

- Quality of life questionnaires
- Fasting Gated FDG-PET scan
- Echocardiography
- Blood draw for flow cytometry, plasma nitrite and nitrate, global arginine bioavailability ratio (GABR), Erythropoietin, & NT-proBNP
- Urine for nitrate
- Exhaled NO

E. Intervention

Open-label Run-in Phase

All enrolled, eligible subjects will receive an open-label carvedilol therapy at starting dose of 3.125 mg twice daily for one week and be monitored at the Clinical Research Unit for the first-dose challenge of Carvedilol. Upon discharge, enough carvedilol to complete the 1-week run-in period will be dispensed by a licensed provider. Subjects will be instructed to return in 1 week with any

unused medication. Those individuals who are eligible for randomization to the trial will undergo the procedures summarized in Table A1 “Run-in Week”.

Double-blinded Randomized Phase

At the end of the 1-week run-in phase, subjects who have tolerated the low-dose carvedilol without severe or limiting side effects, still meet the inclusion and exclusion criteria, and who wish to continue in the study will be randomized to one of three arms: placebo, low-dose carvedilol, or escalating dose carvedilol for 6 months. Subjects and the investigators will be blinded to their group assignment for the duration of the study.

- Group 1 will receive a placebo drug to take twice daily for 6 months.
- Group 2 will receive carvedilol at a dose of 3.125 mg twice a day for 6 months.
- Group 3 will receive carvedilol in a dose escalation scheme. They will be given 3.125 mg tablets to take bid for 1 week, followed by 6.25 mg bid for 1 week, followed by 12.5 mg bid for 1 week with the option to increase to the max dose of 25 mg bid for the remainder of the study. During up titration, if a dose is not tolerated, the dose will be decreased to the previous tolerated dose for the remainder of the study.

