Because study physicians are blinded to groups, if patients are determined to be intolerant of drug (based on symptoms, signs such as sitting systolic BP<85 mm Hg or resting pulse<50, or severe adverse event such as hospitalization for heart failure), a request for dose reduction to the prior week will be requested from the research pharmacist ([name]), who is aware of treatment assignment. He will provide a new week's worth of medications at the “lower” dose. In the case of placebo, placebo will again be provided. In the case of fixed low-dose of carvedilol, placebo will be provided. In the case of dose-escalating carvedilol, the prior week's dose will be provided. Regardless of changes in dose, all three randomized study groups will be compared, based on the intent-to-treat principle, and thus subjects will be maintained in their original assigned study group for analyses.

Randomization scheme

Blocked randomization will be used. The block sizes will also be random and known only to the research pharmacist ([name], Cleveland Clinic Research Pharmacy), who will perform the randomization and know treatment assignment at time of enrollment. The research pharmacist will ensure that a disproportionate subclass (idiopathic, familial or associated PAH) and/or severity of PAH are not entered into any single arm of the study.

Blinded Medication Dispensing

After randomization, all subjects will receive the study medication/placebo for the first 4 weeks in 4 separate bottles labeled “week 1,” “week 2,” “week 3” and “week 4” to blind subjects to whether they are assigned to the dose escalation group. All pills will be encapsulated so that dosing or medication cannot be discerned by patients or study investigators. Enough medication/placebo will be dispensed to last until the next scheduled follow-up visit. Subjects will be instructed to bring all unused medication and the medication bottles (even if empty) to each follow-up visit.

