If any patients in any arm of the study appear intolerant of drug (based on symptoms such as persistent light-headedness, sitting systolic BP<85 mm Hg or resting pulse<50, or hospitalization for heart failure), they will be provided a new bottle of pills labeled “week-dose reduction” as following: subjects on dose-escalating carvedilol will be provided a new bottle of carvedilol at the prior week's dose, subjects on fixed low-dose of carvedilol will be provided placebo pills, subjects on placebo will be provided a new placebo pill bottle. Once dose reduction has occurred in the dose-escalating arm, subjects will be maintained on that set dose throughout the remainder of the study, with no further escalation of dose. If signs or symptoms of subjects in any arm persist despite the dose reduction, dose reduction will again be implemented as follows: subjects on dose-escalating carvedilol will be provided a new bottle of carvedilol at half the current reduced dose, subjects on fixed low-dose carvedilol will again be provided placebo pills, subjects on placebo will again be provided a new placebo pill bottle. Of note, only 3 total dose reductions will be allowed during the entire 6 month study. Following 3 dose reductions are implemented, if subjects are still intolerant, they will be removed from all study drug.

Subject Instruction

All subjects will be advised to take the study medication with a small meal. All subjects will receive a daily phone call for the first week after start of carvedilol during the run-in. Thereafter, patients will be called weekly to screen for side effects and to monitor their clinical status. Patients will be provided a home blood pressure monitoring device and asked to record pulse and blood pressure in the morning and evening at the same time each day with instructions to call at any time systolic BP<85 mm Hg or pulse<55. Lightheadedness is expected to occur, but in 99.5% of cases in prior studies of severe heart failure, this resolves without problems. Patients will be instructed to sit up and rise slowly. Patients will also be instructed to call if they experience any new or worsening symptoms, or require hospitalization or unscheduled doctor visits.

F. Follow-up Schedule

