Baseline characteristics will be reported, including age range and the proportions that are female, postmenopausal, and Caucasian. Means and standard deviations or medians and interquartile range will be reported for all continuous data, and non-continuous data will be reported as percentages. A log transformation may be utilized for any data that is not normally distributed. The three randomized study groups will be compared, based on the intent-to-treat principle, with respect to changes from baseline. Repeated measures analysis of variance will be used to compare groups using data from all time points together, though T-tests will also be used to compare pairs of groups with respect to differences between pairs of time points. Using actual administered doses, relationships between dose and changes over time will also be explored using appropriate linear or non-linear models to estimate dose-response relationships. Reports of blinded group summaries of adverse events will be regularly produced for safety monitoring.

b. Confidentiality

To maintain patient confidentiality, all study data will be de-identified. Each subject, upon enrolling in the study, will be assigned a three-digit subject number. Case report forms and the study database will identify each subject only by subject number and will contain no patient identifiers. De-identified case report forms will be kept within study binders, kept in a locked filing cabinet in a locked room. Completely de-identified study data will be stored in a data table maintained on a password-protected computer and stored on the Cleveland Clinic network, which is regularly backed up. The code identifying which patient belongs to each subject number will be kept in a separate locked filing cabinet in a locked room. Only the study coordinator and investigators will have access to this code.

REFERENCES

1. ATS statement: guidelines for the six-minute walk test. Am J Respir Crit Care Med 2002;166:111-7.

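### The only analysis labelled dose-response uses the dose actually taken, which is set after randomization by tolerability; an ordered contrast over the randomized arms should carry that question

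*Combined protocol and SAP*

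**What the plan says.** Under Data Analysis/Reporting, a. Analysis Plan, the main comparison is randomized: "The three randomized study groups will be compared, based on the intent-to-treat principle, with respect to changes from baseline". It uses repeated measures analysis of variance, with t-tests between pairs of groups. The plan then adds: "Using actual administered doses, relationships between dose and changes over time will also be explored", by linear or non-linear models. The stated purpose is to estimate dose-response relationships. No other analysis in the document carries that label. The plan names no covariates for it, does not say whether dose means last, mean or cumulative dose, and gives no caution on interpretation.

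Section E (Intervention) determines the dose a patient actually takes:

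- In the escalating arm the top step is optional, "with the option to increase to the max dose of 25 mg bid for the remainder of the study", and during titration, "if a dose is not tolerated, the dose will be decreased to the previous tolerated dose".
- Intolerance is judged on symptoms, "signs such as sitting systolic BP<85 mm Hg or resting pulse<50, or severe adverse event such as hospitalization for heart failure".
- Under Blinded Medication Dispensing, an intolerant patient in the fixed low-dose arm is given placebo and a placebo patient stays on placebo. At most three reductions are allowed before study drug is withdrawn.

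Section E also protects the main analysis: "Regardless of changes in dose, all three randomized study groups will be compared, based on the intent-to-treat principle".

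**The concern.** Randomization balances the arms. It does not balance patients who reach 25 mg against patients who stop at 6.25 mg, because that split is made later by how each patient fares. Two features follow from the dosing rules without further assumption. First, the 25 mg level contains only patients who tolerated it, while dose 0 contains placebo patients of every tolerability plus low-dose patients who did not tolerate 3.125 mg. Second, heart-failure hospitalization triggers dose reduction, and hospitalizations are also recorded as outcome information (Secondary Aim, item 3), so exposure is partly defined by the clinical course.

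If the characteristics that lead to dose reduction also predict change in FDG uptake or erythropoietin, a regression of change on dose taken will show a slope without any drug effect. At stake is the interpretation of a result that readers may use to judge whether more drug does more, when three randomized dose strategies can address that question without confounding.

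**Working it through.** **Inputs from section C (Sample Size Rationale and Estimate).** Analysis on log-ratios, 14 per group, coefficient of variation at most 50%, 50% lower median, alpha 0.025, 90% power. Sidedness is not stated; two-sided is assumed.

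**The plan's own figure.** The difference is ln 2 = 0.693.

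- With log SD taken as 0.50: standard error 0.50 × √(2/14) = 0.189, noncentrality 0.693/0.189 = 3.67, 26 degrees of freedom, power 0.894. This matches the stated 90%.
- With log SD = √ln(1 + 0.5²) = 0.472: power at 14 per group is 0.926.

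The sample size is reproduced and is not in question. It supplies the 14 per arm and the 0.472 used below.

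**Simulation with no drug effect.** Each patient has a severity score u. The log-ratio is y = 0.472 × (ρu + √(1 − ρ²)e), with u and e standard normal and no treatment term. Placebo patients have dose 0. The actual-dose model is a straight line of y on dose over all arms, tested two-sided at 5%. That level is a yardstick; the plan sets no test level for this model.

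Assumptions that the documents do not supply: ρ (severity with outcome), the correlation of severity with tolerability, and the final-dose spread in the escalating arm. In the first two rows severity alone sets the dose, and the worst 10% of the low-dose arm move to 0.

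| Severity–tolerability correlation | Escalating arm | ρ = 0 | ρ = 0.3 | ρ = 0.5 | ρ = 0.7 |
|---|---|---|---|---|---|
| 1 | even over 3.125, 6.25, 12.5, 25 mg | 5.1% | 10.3% | 21.4% | 38.4% |
| 1 | half at 25 mg | 5.0% | 8.5% | 14.6% | 24.6% |
| 0.7 | one assumed spread | 5.1% | 7.1% | 11.2% | 17.2% |

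Further settings, for ρ from 0.3 to 0.7:

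- Correlation 0.7 with 80% of the escalating arm reaching 25 mg: 5.7% to 7.6%.
- Correlation 0.2 to 0.3 over three assumed dose spreads: 4.5% to 7.7%.
- Analysis by assigned dose (0, 3.125, 25), run for the settings of the first two rows: 4.9% to 5.3%, mean ratio for 25 mg against 0 of 1.00.

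The table rests on 20,000 trials per setting in the first two rows and 6,000 in the third; the weak-correlation and 80% settings used 3,000. With 3,000 trials the simulation error at 5% is √(0.05 × 0.95/3000) = 0.4 percentage points, so 4.5% is not a real departure from 5%.

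**Why the rows differ.** If tolerability and outcome are linked only through severity, their correlation is the product of the two. In the third row at ρ = 0.7 that is 0.7 × 0.7 = 0.49. Its 17.2% duly falls between the 21.4% and 14.6% of the first two rows at ρ = 0.5. With a severity–tolerability correlation of 0.2 to 0.3 the product is between 0.2 × 0.3 = 0.06 and 0.3 × 0.7 = 0.21, hence rates near nominal.

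**Size of the false gradient.** The mean estimated ratio for 25 mg against 0, at ρ = 0.3, 0.5 and 0.7, is 0.83, 0.73, 0.65 (first row); 0.89, 0.82, 0.76 (second); 0.90, 0.85, 0.80 (third). These are below 1 because the simulation makes sicker patients take less drug and have higher ratios. If the link ran the other way, the rejection rates would be unchanged and the ratios would invert, for example 1/0.83 = 1.20.

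**The case against.** The strongest reply is that the plan already puts the randomized comparison first. Three intent-to-treat group comparisons are available, the actual-dose model comes after them as exploration, and no endpoint, sample size or confirmatory claim depends on it. All of that stands.

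A reader might infer that sicker patients will end on lower doses and that a false gradient favouring higher doses will follow. The documents do not support that as fact. The only statement on severity and tolerability, in the introduction, says that intolerance did not differ between severe and milder heart failure. It concerns left heart failure, but it points away from the inference. The randomized population is also narrowed by the NYHA class I to III criterion, the blood-pressure exclusion and a tolerated run-in week. Low pressure or pulse on a beta-blocker may reflect sensitivity to the drug rather than severity. The introduction links erythropoietin to severity as a level, whereas the analysis concerns change; nothing in the documents links severity to change.

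A reader might also cite the higher rejection rates seen within the escalating arm alone (up to 73.5% in the first setting at ρ = 0.7). The plan describes no such within-arm test, so the all-arm figures are the relevant ones.

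The reply does not remove the main point. Calling a model exploratory does not make it randomized, and this is the only analysis the plan offers under the name of dose-response.

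**Conclusion.** The point holds as an inexpensive improvement in interpretation. It is not a defect in the primary analysis. As written, the dose-response estimate compares groups formed after randomization by tolerability and clinical events, and it can show a slope when the drug does nothing. Whether it would do so here, how strongly and in which direction depends on correlations that the documents do not give. Under the assumptions shown, the all-arm false-positive rate at nominal 5% runs from about 5% with weak correlations, or when most of the escalating arm reaches the top dose, to 17% to 38% with strong ones. Analysis by assigned arm stays at about 5% whatever the correlation, because it uses only the randomized assignment. It would be wrong to conclude that the intent-to-treat comparisons or the sample size are compromised.

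**What to change.** In the Analysis Plan, name as the main dose-response analysis an ordered contrast over the randomized arms (placebo, fixed low dose, escalating) within the planned repeated-measures comparison of changes, on log-ratios for FDG uptake and erythropoietin. Table 1 schedules FDG-PET only at baseline and month 6, so for uptake this is a contrast on one log-ratio per patient; erythropoietin also has month 3.

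Fix the contrast scores before unblinding, because they matter. Equally spaced scores (−1, 0, +1) with equal arms reduce to escalating minus placebo. Scores of 0, 3.125 and 25 have mean 28.125/3 = 9.375 and give weights −9.375, −6.25 and +15.625.

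Keep the actual-dose model as description only. Define its dose metric (last, mean or cumulative), label it non-randomized, and state that adjusting for baseline severity does not remove confounding by events after randomization.

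The cost is one added contrast and a few sentences, with no new data, visits or patients. The drawback is that the contrast describes assigned strategies and not milligrams taken.
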